WHO	World Health Organization

PROTOCOL SUMMARY

- Title:** Natural History of Infection Caused by BK Virus (and other Opportunistic Viral Pathogens) in Renal and Renal-Pancreas Transplant Recipients
- Phase:** Not Applicable (Natural History Study)
- Study Population:** Male and female renal or renal-pancreas transplant recipients at risk for BK virus infection
- Sample Size:** Approximately 450 subjects will be enrolled for screening for BK viremia (15% over-enrollment allowed, to a maximum of 518 screened subjects) to allow identification of approximately 40 (to a maximum of 60) subjects with viremia.
- Number of Sites:** Approximately 6
- Study Duration:** 3 years
- Subject Participation Duration:** Maximum of 24 months
- Objectives:**
- Primary Objectives:**
- To establish the natural history of BK viremia in a multicenter population of renal and renal/pancreas transplant patients, to include incidence, time to onset, duration, and quantitation of viral load;
 - To assess associations between BK viremia and decline in GFR in renal transplant recipients.
- Secondary Objectives:**
- To define the donor and recipient-related risk factors for BK viremia and BKVN in a multicenter population of renal and renal-pancreas transplant patients;
 - To define the frequency of clinical outcomes that are potentially related to BKV infection.
- Tertiary (Exploratory) Objectives:**
- To compare quantitative measurements of BKV DNA by PCR in plasma and (when appropriate) in urine, in order to determine biologic significance;
 - To assess plasma for evidence of other opportunistic viral pathogens, including CMV, EBV, HHV-6, and adenovirus;
 - To assess urine for evidence of other opportunistic viral pathogens, including CMV and adenovirus;

- To compare quantitative BKV PCR results from each site (local or reference laboratory) with matched results from the Central Unit laboratory;
- To explore the potential of biomarkers of tubular injury for predicting increased risk of BKVN;

[figure not shown]
Description of Study Design:

The primary objective is to define the natural history of BK viremia. In order to understand the natural history of infection, we will measure the time (days post-transplant) to the development of BK viremia and its correlation with progression to end-organ disease (BKVN or BK hemorrhagic cystitis). Data from this prospective monitoring will allow for the identification of the types of high-risk patients who might benefit from future studies of therapeutic interventions for BKV infection (when effective therapy becomes available). This will be accomplished by serial quantitative BK DNA measurements in blood (plasma), assayed by polymerase chain reaction (PCR). Phases of the study can be summarized as follows:

- Subject identification and informed consent. Informed consent should be obtained early in the peri-transplant period (between 7 days pre-transplantation [T-7d] and 100 days post-transplantation [T+100 d]).
- Prospective screening for BK viremia. Enrollment and initiation of specimen collection should begin no sooner than 4 weeks after transplantation. Enrollment cannot occur later than 100 days after transplantation. Subjects will be screened (collection of blood and urine for laboratory studies, including BK PCR) approximately monthly for 6 months (timed from the date of transplantation), then every other month for 6 months. For those subjects who remain BKV-negative, screening will terminate approximately 12 months from the date of transplantation.
- Intensive sampling of subjects identified with BK viremia. Subjects identified with qualifying viremia will be sampled approximately every two weeks until resolution of viremia (defined as PCR negative, or <1000 copies/ml).
Note: Patients who did not participate in the prospective screening phase but are identified with BK viremia by standard-of-care testing may be enrolled, as long as they are still within 100 days of transplantation.
- Post-viremia follow-up. Following resolution of viremia, subjects will be sampled (collection of blood and urine) approximately monthly for 6 months (unless another termination event occurs sooner).

SCHEMATIC OF STUDY DESIGN

DMID Protocol # 11-0071 Active Screening/Natural History Phase

2. BACKGROUND INFORMATION AND SCIENTIFIC RATIONALE

2.1. Background Information

2.1.1. BK Virus (BKV) and BKV-Associated Nephropathy (BKVN)

BK virus (BKV) is a small (45 to 55 nm) non-enveloped polyoma virus, having a circular double-stranded DNA (dsDNA) genome with approximately 5,000 base pairs. BKV was first isolated in 1970 from a renal transplant patient (initials "BK") with ureteral stenosis. Seroepidemiologic studies have demonstrated that BKV infection is virtually universal and that asymptomatic primary infection occurs in early childhood. In a healthy Swiss cohort aged 20-59 years, the seroprevalence for BKV was 82%.¹ Following primary infection, BKV appears to preferentially establish latent infection in the genitourinary tract. Four distinct genotypes of BKV have been identified which have varying geographic distributions and may not all be equally pathogenic in the setting of organ transplantation. In addition, recent studies suggest that the 4 genotypes may also be serologically distinct.

BKV rarely causes disease in immunocompetent adults, but in the setting of immunosuppression (such as renal transplantation) BKV can reactivate and cause asymptomatic viremia or symptomatic disease. The donor kidney also appears to be an important source of BKV infection in the graft recipient. Studies have shown that the higher the BKV antibody titer in the donor, the greater the incidence of BKV disease in the renal transplant recipient.² BKV nephropathy (BKVN) and ureteral stenosis are the most commonly described clinical manifestations of BKV infection in renal transplant recipients.³ Hemorrhagic cystitis due to BKV, another common manifestation, is observed most often in hematopoietic stem cell transplant (HSCT) patients, but occurs in renal transplant patients as well.

BK polyomavirus infection is mediated by direct infection of allograft renal tubular epithelial cells (TECs). Molecular analysis has demonstrated that there is substantial inflammatory injury associated with a profibrotic milieu.¹⁶ Monitoring for infection is performed by detecting viral copies in urine and blood. However, virus is frequently shed in the urine in the absence of invasion leaving the urinary monitoring as a suboptimal screening mechanism in terms of management of recipients that are infected. A testable hypothesis is that tubular injury, in the context of viral infection, indicates invasive disease. Detection of this tubular injury may provide an opportunity to manage kidney graft recipients at an earlier stage before invasive BK disease. Coupled with urine PCR, detection of renal tubular injury in recipient urine is a simple technique. Urine markers of injury have already been identified in other causes of acute kidney injury and are commercially available. These include cystatin C, renin, clusterin, Kim-1, b2-microglobulin, osteopontin, retinol binding protein, and markers of cell apoptosis.

Currently, no antiviral drug is approved for treatment of BKV infection.¹⁷ Anecdotal reports have claimed benefit from cidofovir, leflunomide, quinolone antibiotics, and intravenous immunoglobulin. However, the current standard of care is early screening for BKV viremia and reduction in immunosuppressive therapy in an effort to improve graft survival, although it has not been studied in a controlled fashion.^{12,18,19} At some institutions, modulation of immunosuppressive therapy has dramatically reduced the rate of allograft loss due to BKVN.¹⁴ Reduction in the immunosuppressive regimen is not without consequence and can result in graft loss from immune-mediated organ rejection.²⁰ Despite reduction in immunosuppression, in some studies 30 to 70% of patients with BKVN have progressive deterioration in renal function, eventually resulting in allograft loss. Declining renal function typically occurs over months and is thought to result from a combination of persistent viral infection, organ rejection (induced by reduction in immunosuppression), and renal fibrosis.

This study is being performed to identify the natural history of BK viremia in renal transplant patients with the intent to identify high-risk groups that may benefit in the future from therapy with

safer and more effective antiviral medications.

2.2. Scientific Rationale

Renal or renal-pancreas transplant patients are at high risk of significant consequences from BKV infection, but have limited treatment options. No antiviral therapies of proven clinical value are currently available to treat BKV infection. The natural history of infection in this population is incompletely understood. Thus, BKV-infected renal or renal-pancreas transplant patients have been selected for inclusion in this study as they are an at-risk patient population with an unmet medical need.

2.2.1. Renal (or Renal-Pancreas Transplant) Patients

Approximately 30 – 60% of all renal or renal-pancreas transplant patients will have detectable levels of BKV DNA in their urine in the post-transplant period. Approximately 10 – 15% of renal transplant patients will have BK viremia. Among the patients who progress to BKVN, virtually all will have BK viremia. Predictors of viremia include early onset of BK viruria, rapid increase in quantitative viruria, and high peak titers of BKV DNA in urine. In an effort to capture these subjects early in the course of the evolving BK infection and avoid subjects who have already developed evidence of BKVN, this protocol will emphasize the initiation of screening in the early post-transplant period. In addition, since BKVN tends to occur most frequently within the first six months after transplantation, screening will be more frequent early in the post-transplant period.

2.3. Potential Risks and Benefits

2.3.1 Potential Risks

There are no potential risks to participants, other than the minimal risk associated with routine phlebotomy. Most data and specimens can be timed for collection at the participants' standard-of-care clinic visits. There are no potential benefits for an individual volunteering to take part in this natural history study, other than contributing to a better understanding of an infectious disease for which he/she is at risk. The participant will be allowing the research to collect data and residual blood samples that can be used to research BK infection and provide potentially useful data for monitoring and treatment of future transplant patients.

2.3.2. Potential Benefits

There may not be any direct benefit for individual subjects enrolled in this study. Some study specimens will be batch-shipped and processed, so results will not always be available to inform the subjects' clinical management. Indirectly, the data from this study will teach the transplant community when interventions are most likely to be successful.

3. OBJECTIVES

3.1. Study Objectives

3.1.1. Primary Objectives

- To establish the natural history of BK viremia in a multicenter population of renal and renal/pancreas transplant patients, to include incidence, time to onset, duration, and quantitation of viral load;
- To assess associations between BK viremia and decline in GFR in renal transplant recipients.

3.1.2. Secondary Objectives

- To define the donor and recipient-related risk factors for BK viremia and BKVN in a multicenter population of renal and renal-pancreas transplant patients;
- To define the frequency of clinical outcomes that are potentially related to BKV infection.

3.1.3. Tertiary (Exploratory) Objectives

- To compare quantitative measurements of BKV DNA by PCR in plasma and, when appropriate, in urine, in order to determine biologic significance;
- To assess plasma for evidence of other opportunistic viral pathogens, including CMV, EBV, HHV-6, and adenovirus;
- To assess urine for evidence of other opportunistic viral pathogens, including CMV and adenovirus;
- To compare quantitative BKV PCR results from each site (local or reference laboratory) with matched results from the Central Unit laboratory;
- To explore the potential of biomarkers of tubular injury for predicting increased risk of BKVN.
- Relationship of development of BKVN with immunosuppressive therapy

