3.2.3. Exploratory Endpoints

- Frequency of BK viruria (incidence, time of onset, duration, viral load quantitation by PCR) in subjects with and without BK viremia

- Frequency of CMV, EBV, HHV-6, and adenovirus viremia at multiple time points in subjects with and without BK viremia
- Frequency of CMV and adenovirus viruria at multiple time points in subjects with and without BK viremia
- Results of BK PCR assays performed on matched specimens at the participating sites (local or reference laboratories) and at the UAB Central Laboratory
- Results of urinary biomarkers of tubular injury measured at multiple time points in subjects with and without viremia, including any subjects with BKVN. Potential urinary biomarkers include cystatin C, renin, clusterin, Kim-1, b2-microglobulin, osteopontin, retinol binding protein, and markers of cell apoptosis. Urine biomarkers will not be resulted in real-time.

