4.2. Prospective Screening Phase

Approximately 450 subjects will be screened for BK viremia (15% over-enrollment allowed, to a maximum of 518 screened subjects). During the screening phase, subjects will submit blood (plasma) for quantitative measurement of BKV DNA approximately every 4 weeks, ± 7 days, for 6 months (timed from the date of transplantation) and then approximately every 8 weeks, ± 14 days for 6 months. Also, urine specimens will be collected at each visit and stored for subsequent testing. During the screening phase, the specified intervals between sample collections should be followed as closely as possible, but may vary with subject availability. If qualifying BK viremia is not detected, surveillance will terminate approximately 12 months after the date of transplantation (or when another study termination endpoint is reached, whichever occurs sooner).

NOTE: BKV PCR results of $\geq 10,000$ from the study central laboratory, the site laboratory, or a reference laboratory are acceptable to qualify the patient for inclusion in the Intensive Monitoring Phase of the study.

NOTE: Non-study patients who are determined to have a qualifying blood BK viral load ($\geq 10,000$ copies/ml) during the course of routine clinical care (i.e., patients not consented and not identified by prospective screening/surveillance) will also be eligible for enrollment directly into the intensive monitoring surveillance phase after providing consent as long as they remain within the window of ≤ 100 days following transplantation.

Subjects will remain in the screening/surveillance phase: 1) for 12 months post-transplantation; 2) until qualifying BK viremia is documented; 3) until renal graft failure, re-transplantation, and/or initiation of chronic dialysis occurs; 4) death; 5) until subject decides to terminate participation; 6) until the investigator decides that the subject should terminate participation; or 7) until the study closes (whichever occurs first). Reason for termination of participation in the study will be documented.

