8.4. Final Analysis Plan

All statistical tests will be performed at 5% significance level and confidence interval at 95% level. There will be no adjustment on the levels for multiple testing. There will also be no imputation methods that will be used for missing data. Any viral load <100 (i.e., undetectable) will be replaced by viral load value of 10. Quantitative viral loads will be analyzed based on the log based 10 transformation.

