8.4.3. Exploratory Endpoints

To investigate the association between the incidence between BK viremia and BK viruria, we will utilize the Fisher's exact test or the large-sample chi-squared test for association whichever is applicable. Time to onset and duration of BK viremia and BK viruria will be analyzed using survival analyses.

Logistic regression will be utilized to determine if other viruses such as CMV, adenovirus, etc. are risk factors for BK viremia. This tool will also be used to determine if selected urinary biomarkers of tubular injury are predictors of BKVN.

To assess the relationship of the time to development of BKVN with the use of immunosuppressive therapy, we will use survival regression analysis with the length of use of immunosuppressive weighted by dose as a predictor variable of interest.

Finally, to examine the reproducibility of the quantitative PCR assays at the participating sites and PCR assays at UAB, we compute the differences in the results and construct a 95% confidence interval for the mean difference. We will also create a Bland-Altman plot which will display the differences and their 95% confidence intervals as a function of the mean readings of the two PCR results.

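### The laboratory-agreement objective is set for each site, but section 8.4.3 describes one mean difference with no by-laboratory step, which can dilute or cancel laboratory offsets

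*Combined protocol and SAP*

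**What the plan says.** The objective, in the Protocol Summary and again in section 3.1.3, is framed by laboratory: "To compare quantitative BKV PCR results from each site (local or reference laboratory) with matched results from the Central Unit laboratory". The matching endpoint in section 3.2.3 is "Results of BK PCR assays performed on matched specimens at the participating sites (local or reference laboratories) and at the UAB Central Laboratory"; it names no summary by laboratory.

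Section 8.4.3 contains the only analysis. Its numerical part is "we compute the differences in the results and construct a 95% confidence interval for the mean difference". Its graphical part is "We will also create a Bland-Altman plot which will display the differences and their 95% confidence intervals as a function of the mean readings". Neither carries a site or laboratory term, and no limit of acceptable agreement is set. The general rules in section 8.4 add the scale ("Quantitative viral loads will be analyzed based on the log based 10 transformation") and the 95% level, but nothing about laboratories.

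Three other facts bear on the point. The Protocol Summary expects about six sites; the number of distinct laboratories is not given. Under section 7.5, local or reference results are recorded when the test was done for standard of care, so the number of pairs per laboratory is not controlled. Under section 4.2, results at or above 10,000 copies/ml "from the study central laboratory, the site laboratory, or a reference laboratory are acceptable to qualify the patient" for the intensive phase.

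**The concern.** The objective asks about each laboratory; the analysis as written gives one figure for all of them. If laboratories differ systematically from the central assay, the single mean is an average of their offsets, weighted by how many pairs each contributes. An offset in one laboratory is diluted, and offsets in opposite directions cancel. A mean near zero could then be read as agreement when individual laboratories do not agree.

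What is at stake is the interpretation of local results. A local or reference value can move a subject into the intensive phase, so the offset that matters for such a subject is that of the laboratory that produced the value. The pooled mean does not give it.

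**Working it through.** The plan states no sample size, SD or agreement limit for this comparison, so there is no figure of its own to reproduce.

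**Inputs from the documents:** log10 scale and 95% level (section 8.4); about six sites (Protocol Summary).

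**Assumptions, not in the documents:** one laboratory per site (6); 20 pairs per laboratory, all positive and independent; within-laboratory SD of the log10 difference 0.3; illustrative offsets.

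**Formulas.** With offset b_i and n_i pairs in laboratory i, and N pairs in all:

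- pooled mean = Σ n_i b_i / N
- pooled SD = √(within-laboratory SD² + variance of the offsets)
- half-width of the pooled interval = t × pooled SD / √N
- half-width for one laboratory = t × within-laboratory SD / √n_i

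**Case 1: three laboratories at +0.5, three at -0.5.**

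- Each laboratory is 10^0.5 = 3.2-fold high or low. A local reading of 10,000 then corresponds to a central value of about 10,000/3.162 = 3,162 or 10,000 × 3.162 = 31,623.
- Pooled mean: (3 × 0.5 - 3 × 0.5)/6 = 0.00.
- Pooled SD: √(0.3² + 0.5²) = √0.34 = 0.583.
- Pooled half-width: 1.98 × 0.583/√120 = 0.105, or 0.78- to 1.27-fold.
- One high laboratory alone: 0.5 ± 2.093 × 0.3/√20 = 0.5 ± 0.14, that is 0.36 to 0.64, or 2.3- to 4.4-fold high.
- Limits of agreement over all pairs: ±1.96 × 0.583 = ±1.14 log10.

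This was also simulated (4,000 datasets per scenario) with 10 to 50 pairs per laboratory and within-laboratory SD 0.2 to 0.4. The pooled interval included zero in at least 99.8% of datasets. The interval for one laboratory included zero in 0% to 6%.

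**Case 2: offsets that do not balance.**

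- Four laboratories at +0.5 and two at -0.5: pooled mean (4 × 0.5 - 2 × 0.5)/6 = 0.17, or 1.5-fold, although all six are 3.2-fold off.
- One laboratory at +0.7 (5-fold) and five unbiased: pooled mean 0.7/6 = 0.117, or 1.3-fold, interval 0.045 to 0.189. This interval included zero in only 5% of datasets, so a difference would usually be flagged, but its size understates that laboratory's offset.

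Dilution is therefore the general result, and full cancellation the extreme one.

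**Is the pooled interval too narrow?** For the mean over the six participating laboratories in case 1, the sampling error comes only from within-laboratory variation: 0.3/√120 = 0.027, a half-width of 1.96 × 0.027 = 0.054. The pooled interval uses 0.105, because the offsets inflate its SD, so it is wider than needed. In 20,000 simulations with random offsets of SD 0.2, 0.3 and 0.5 log10, it covered the mean over the participating laboratories 97.5%, 98.8% and 99.7% of the time.

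**The case against.** **Pooling is inferred.** Section 8.4.3 never says that the laboratories are combined, and it does not forbid a by-site analysis. This stands. The defect is that the text, followed literally, yields one figure and requires nothing else.

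**The Bland-Altman plot would reveal the disagreement.** In case 1 the points would lie around +0.5 and -0.5, with limits of agreement near ±1.14 log10, which nobody would take for good agreement. This stands in part. The plan names confidence intervals, not limits of agreement, and does not mark the laboratory. The scatter would show spread without separating random error from particular laboratories. A reader might infer that the plan would certainly report discordant laboratories as agreeing. The documents do not support that: no agreement criterion is set, and the inference requires reading the mean alone.

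**Full cancellation is a special case.** It needs opposite offsets with about equal weight. With random offsets of SD 0.2, 0.3 or 0.5, the pooled interval excludes zero in about 46%, 57% and 64% of simulations. This stands.

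**A reader might also infer that the pooled interval under-covers.** It would do so, badly, as a statement about a wider population of laboratories. But sections 3.1.3, 3.2.3 and 8.4.3 concern the participating sites, and for their mean the interval is conservative.

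**The link to the 10,000 threshold is limited.** The comparison belongs to the final analysis and cannot change who entered the intensive phase. Under section 7.5, plasma also goes to the central laboratory for real-time assay, except during post-viremia follow-up. Nothing here shows a bias in the incidence estimate.

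**The inputs are assumed.** Distinct assays, the offsets and 20 pairs per laboratory are not in the documents, and sites may share a reference laboratory.

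**Conclusion.** The mismatch is real: the objective is stated for each site, and the only analysis described has no by-laboratory step. Taken literally, it cannot answer the objective. Under the assumed values, it can return a mean of 0.00 with an interval of about ±0.10 log10 while every laboratory is 3.2-fold off, or shrink one laboratory's 5-fold offset to 1.3-fold. How far this would happen in the study depends on between-laboratory differences and pair counts that the documents do not give.

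The point goes no further than that. It does not establish that the interval is too narrow for the participating laboratories, that disagreement would go unseen, or that any primary or secondary result is affected. Severity is minor, since the objective is exploratory; this is a cheap improvement.

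**What to change.** In section 8.4.3:

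- Report the mean log10 difference from the central laboratory, its 95% confidence interval and the limits of agreement separately for each laboratory, whether site or reference.
- Identify the laboratory on the Bland-Altman plot, by symbol or by panel.
- If an overall figure is given, report the between-laboratory SD beside it. Use a random laboratory effect only if inference to other laboratories is wanted, and then with small-sample degrees of freedom. With six laboratories (5 df, t = 2.57), 20 pairs each and SD 0.3, the half-width is 2.57 × √(SD_lab²/6 + 0.3²/120), which is 0.22, 0.32 or 0.53 log10 for a between-laboratory SD of 0.2, 0.3 or 0.5.

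The cost is a few lines of text and minor programming, with no extra visits or specimens. The laboratory that ran each local result must be recorded; the documents do not say whether the eCRF captures this. Laboratories with few pairs will have wide intervals, which is a fair picture of what the data can say about them.
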